11 INTERIM AND DMC ANALYSES

11.1 Interim Analysis

In the protocol it has been mentioned that IA may take place at any time during the study at the discretion of the sponsor to support regulatory and/or reimbursement dossiers. An interim analysis was conducted when the last subject reached Part A Week 24. The analysis details of the Week 24 interim analysis were provided in Section 11.1.1 below. Another IA will be conducted when the last subject reaches Part B Week 48, i.e., Week 144 in the OLE study. The analysis details of the Week 144 IA are provided in Section 11.1.2. Unless specified otherwise, the general rules, principles, and scopes specified in Section 10 apply to the IAs.

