11.1.2 Week 144 Interim Analysis

The following efficacy endpoints will be analyzed using methods specified in Section 10.3.2.2.2. Both MMRM models and descriptive summaries will include data up to the OLE Part B Week 48 (inclusive) analysis visit. The windowing rules are provided in Appendix B.

- Absolute change in percent predicted forced expiratory volume in 1 second (ppFEV₁)
- Absolute change in sweat chloride (SwCl)
- Absolute change in CFQ-R respiratory domain (RD) score
- Absolute change in body mass index (BMI) and BMI-for-age z-score
- Absolute change in lung clearance index_{2.5} (LCI_{2.5})

- Absolute change in weight and weight-for-age z-score
- Absolute change in height and height-for-age z-score
- Pulmonary Exacerbation (PEx) and CF-related hospitalizations

The study is conducted during the COVID-19 pandemic. If extra assessments (e.g., unscheduled visits) will be collected to mitigate the impact of COVID-19 pandemic on this Week 144 IA, Extended OLE Part B Week 48 analysis visit may replace the regular OLE Part B Week 48 analysis visit for efficacy analysis, using the exact same analysis methods. In such situations, MMRM models with the regular OLE Part B Week 48 analysis visit may be conducted as additional analysis. All efficacy analysis for the Week 144 IA will be based on clinical assessed data.

The same definition on analysis period as described in Section 9 applies to this IA but the analysis period does not exceed the IA data cutoff date. The descriptive summary tables for continuous safety endpoints will stay with the regular visit windowing rule defined in Appendix A and will be restricted to the last visit at which the number of subjects is at least 10. For AE, PEx, similar event base parameters, all available data will be included.

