a. If no numerical measurement is available within a visit window, the measurement will be considered missing for the visit.			
b. If there is more than 1 numerical measurement available within a visit window, use the following rules:			
i. The measurement closest to the target day will be used; or			
ii. If there are multiple measurements with the same distance from the target day, the latest measurement will be used. If the latest measurement cannot be determined, then unscheduled visit will be selected.			
³ For measurement collected on the date of first dose of study drug in Treatment Period, if it cannot be determined whether the measurement is before or after the first dose:			
1. Scheduled measurement will be treated as pre-dose observation.			
2. Unscheduled measurement will be treated as post-dose observation.			
⁴ For safety Assessment, Safety Follow-up analysis visit will be based on nominal Safety Follow-up visit. If a subject doesn't have a nominal Safety Follow-up visit but has an ETT visit with study day >687, then the ETT visit will be mapped into Safety Follow-up analysis visit.			
⁵ For efficacy assessment, if a subject has nominal safety follow up visit with study day >687, then nominal Safety Follow-up visit will be mapped to Safety Follow-up visit; else if subject doesn't have a nominal safety follow-up visit with study day > 687 but has an ETT visit with study day >687, then the ETT visit will be mapped into Safety Follow-up analysis visit; else if there are multiple assessments with >687 then select the earliest record.			
Derived Variables:			

Table 13-1 Analysis Visit Windows for Safety and Efficacy Assessments for Part A			
Assessment	Visit¹	Target Study Day	Analysis Visit Window (in study days)²
1. Age (in years) at first dose date and post-baseline visit (for demographics, listing and the calculation of [percent] predicted spirometry variables):			
Obtain the age at informed consent in “yy, mm” format (e.g., 24 years, 6 months) in parent study from the Vital Signs (VS) page at the Screening Visit in parent study and add 0.5 month to convert to days.			
Obtain the informed consent date in parent study.			
Then age (in years) at first dose or post-baseline visit = [(first dose date or post-baseline visit date – informed consent date in parent study) in days + age at informed consent (in days) in parent study]/365.25.			
2. Age (in months) at first dose date and post-baseline visit (for use in calculation of BMI):			

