⁶ For efficacy assessment in Part B, if a subject has nominal Part B safety follow up visit with study day >1359, then nominal Safety Follow-up visit will be mapped to Safety Follow-up visit; else if subject doesn't have a nominal safety follow-up visit with study day >1359 but has an ETT visit with study day >1359, then the ETT visit will be mapped into Safety Follow-up analysis visit; else if there are multiple assessments with >1401 then select the earliest record.			
Derived Variables: See Table 13-1 .			

Table 13-3 Efficacy Analysis Visit Windows for Week 144 Interim Analysis if Extended OLE Part B Week 48 is used.			
Assessment	Visit	Target Study Day	Analysis Visit Window (in study days)
Efficacy Assessment			
Part A: same as in Table 13-1			
Part B: see below			
Spirometry Weight, Height and BMI (and the corresponding z-scores)	Baseline OLE Part B Week 12 OLE Part B Week 24 OLE Part B Week 36 Extended OLE Part B Week 48	1 757 841 925 1009	defined in section 8.1 (667, 799] (799, 883] (883, 967] >967
CFQ-R	Baseline OLE Part B Week 24 Extended OLE Part B Week 48	1 841 1009	defined in section 8.1 (667, 925] >925
Sweat chloride Lung Clearance Index	Baseline OLE Part B Week 24 Extended OLE Part B Week 48	1 841 1009	defined in section 8.1 (667, 925] >925
Notes: The above analysis windows will be used only when mitigation plans regarding the impact of COVID-19 pandemic will be implemented. See Section 11.1.2 for details.			
See Table 13-1 table notes for detailed.			

▪ Appendix B: Imputation Rules for Missing Prior/Concomitant Medication Dates

Imputation rules for missing or partial medication start/stop dates are defined below:

1. Missing or partial medication start date:
 - a. If only DAY is missing, use the first day of the month.
 - b. If DAY and Month are both missing, use the first day of the year.
 - c. If DAY, Month and Year are all missing, use a date before the first dose date (in practical, use Jan. 01, 2000 to impute).
2. Missing or partial medication stop date:
 - a. If only DAY is missing, use the last day of the month.
 - b. If DAY and Month are both missing, use the last day of the year.
 - c. If DAY, Month and year are all missing, assign ‘continuing’ status to stop date (in practical, use Dec. 31, 2050 to impute).

In summary, the prior, concomitant, or post categorization of a medication is described below.

Table 13-4 Prior, Concomitant, and Post Categorization of a Medication

Medication Start Date	Medication Stop Date		

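### At the Week 144 interim, the COVID-19 extended Part B Week 48 window has no upper study day, so a later scheduled visit can stand in for a missing Week 48 value

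*SAP*

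**What the plan says.** SAP 11.1 sets the timing: "Another IA will be conducted when the last subject reaches Part B Week 48". SAP 11.1.2 then gives a condition, "If extra assessments (e.g., unscheduled visits) will be collected to mitigate the impact of COVID-19 pandemic on this Week 144 IA", under which the "Extended OLE Part B Week 48 analysis visit may replace the regular OLE Part B Week 48 analysis visit for efficacy analysis". In that case, "MMRM models with the regular OLE Part B Week 48 analysis visit may be conducted as additional analysis". It limits the models to data through the Part B Week 48 analysis visit and to assessments made in clinic, and it adds that "the analysis period does not exceed the IA data cutoff date".

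Table 13-3 in Appendix A holds the extended windows. For spirometry, weight, height and BMI the last three read "799, 883] (883, 967] >967"; for CFQ-R, sweat chloride and LCI the last is >925. No later visit is listed. A note restricts the table: "The above analysis windows will be used only when mitigation plans regarding the impact of COVID-19 pandemic will be implemented". It refers to the Table 13-1 notes for the selection rule, under which "The measurement closest to the target day will be used".

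In Table 13-2 the regular Part B Week 48 windows are (967, 1051] and (925, 1093]. SAP 9.3 ends the efficacy period at the Part B Week 96 Visit or, without that visit, at Day 1345 or the end of participation if earlier.

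**The concern.** The extended visit exists to catch make-up assessments, but as printed it also takes in ordinary scheduled visits after Week 48. Table 13-3 has no rows for Weeks 60 to 96, so any later clinic value falls under the Week 48 label. Limiting the models to the Week 48 analysis visit therefore does not keep later data out.

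The condition that triggers the table is also one that creates gaps. Subjects who could not travel may have no clinic value near Week 48, and this interim uses clinic assessments only. A later clinic visit would then fill the gap. The final analysis would report the same measurement at another visit, so the two reports could differ at the same labelled visit.

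The wording also leaves open whether the extended visit replaces the regular one once the condition is met, and whether the regular-window model is shown. No threshold or decision date is given. SAP 11.1 says interim analyses may support submissions to regulators and payers, so a reader needs to know what the Week 48 estimate contains.

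**Working it through.** **Inputs.** Extended windows: SAP Table 13-3. Regular and final-analysis windows: Table 13-2. Selection rule: Table 13-1, note 2. Part B schedule: Protocol Table 3-2. Caps: SAP 9.3 and 11.1.2. Not in the documents, so assumed: enrolment spread *s* (0 to 52 weeks between first and last subject), growth of 5.5 cm/year, and 5% to 15% of subjects affected.

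**1. Reproduce the target days** (7 × OLE weeks + 1).
- Part B Week 48: 7 × 144 + 1 = 1009, as printed.
- Week 60: 7 × 156 + 1 = 1093. Week 72: 7 × 168 + 1 = 1177. Week 96: 7 × 192 + 1 = 1345. All match Table 13-2.

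**2. Can a late value displace an in-window value?**
- Spirometry and growth: the regular window (967, 1051] reaches at most 1051 − 1009 = 42 days from target. The first day beyond it is 1052 − 1009 = 43 days away.
- CFQ-R, sweat chloride, LCI: the window (925, 1093] reaches at most 84 days; the first day beyond is 85 days away.

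The closest value wins, so a late value never displaces an in-window one. The open end matters only for subjects with no regular-window value.

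**3. Which scheduled visits can fill the gap?**
- Spirometry and growth are scheduled every 12 weeks in Part B, so the first candidate is Week 60 (Day 1093). In the final analysis that day lies in (1051, 1135], which is Week 60.
- CFQ-R, sweat chloride and LCI are scheduled at Weeks 24, 48, 72 and 96, so the first candidate is Week 72 (Day 1177). In the final analysis that day lies in (1093, 1261], which is Week 72.

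**4. How late can a value be?** If the cutoff falls when the last subject reaches Day 1009, a subject enrolled *s* weeks earlier has reached Day 1009 + 7*s*, capped at 1345. Maximum lateness is min(*s*, 48) weeks.

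| Spread *s* | Latest day | Past Day 1051 (spirometry, growth) | Past Day 1093 (CFQ-R, sweat chloride, LCI) |
|---|---|---|---|
| 6 weeks | 1051 | 0 | 0 |
| 12 weeks | 1093 | 6 weeks | 0 |
| 24 weeks | 1177 | 18 weeks | 12 weeks |
| 36 weeks | 1261 | 30 weeks | 24 weeks |
| 48 weeks or more | 1345 | 42 weeks | 36 weeks |

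**5. Size for raw height.** Shift in the mean is approximately (fraction affected) × (rate) × (days late / 365.25).
- Week 60 value: 1093 − 1009 = 84 days; 5.5 × 84 / 365.25 = 1.26 cm per affected subject. At 5%, 0.05 × 1.26 = 0.06 cm; at 15%, 0.15 × 1.26 = 0.19 cm.
- For scale, growth over the 144 OLE weeks at that rate is 5.5 × 1008 / 365.25 = 15.2 cm, so the shift is about 0.4% to 1.3% of it.
- No missing Week 48 value: shift zero.

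**The case against.** The window is not unbounded and its use is not unconditional. Both 11.1.2 and the Table 13-3 note tie it to COVID-19 mitigation, and the data cutoff and efficacy period cap it. It adds values only for subjects who would otherwise be missing. Raw height is close to a worst case, because z-scores and percent-predicted values use age at the visit. The continuous safety summaries keep the regular windows, and the final analysis is untouched. All of this stands and limits the size of the point.

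It can also be said that the order of the analyses is implied, since the regular-window model is called the additional one. The Week 24 interim did use the extended visit for the main analysis and ran the regular window alongside (SAP 11.1.1). For Week 144, however, both steps are only permitted.

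A reader might infer that the sponsor could choose between the two estimates after seeing them. The documents do not show this: SAP Section 4 requires Version 3.0 and any revision to precede the interim cutoff. What remains is that an option already written in the plan needs no revision to exercise, so that timing rule does not settle the choice.

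**Conclusion.** The point holds as a defect of specification with a small plausible effect. If Table 13-3 is triggered, a subject without a regular-window value can have a scheduled later value reported as Week 48. The enrolment spread decides whether this can occur: not at about 6 weeks, for spirometry and growth only at about 12 weeks, and for all the continuous efficacy endpoints at about 24 weeks. With Week 60 values from 5% to 15% of subjects at 5.5 cm/year, mean raw height change moves about 0.06 to 0.2 cm. Only secondary efficacy endpoints at this interim are affected.

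Two stronger readings are not supported. A reader might infer that values 48 weeks late will be reported as Week 48. That is a ceiling (1345 − 1009 = 336 days) and needs an enrolment spread of at least 48 weeks, which the documents do not give. A reader might also multiply that ceiling through to a mean height shift of roughly 0.25 to 0.8 cm. Because the closest value wins, that would need 5% to 15% of subjects to have no usable height at Weeks 48, 60, 72 and 84 and then return at Week 96; nothing in the documents suggests this.

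**What to change.** - **Table 13-3.** Give the extended visit a stated upper day before the next scheduled visit for that assessment, or exclude values from later scheduled visits. For spirometry and growth the limit must precede the Week 60 visit. With ±5 days at both Part A Week 96 and Part B Week 60, that visit can fall as early as 673 − 5 + 420 − 5 = Day 1083, so excluding by scheduled visit may be the cleaner rule. For CFQ-R, sweat chloride and LCI, go no later than the regular limit of Day 1093 unless an unscheduled COVID-19 make-up assessment falls later. A limit at Day 1135, the end of the regular Week 60 window, would not do, because Week 60 values would still be labelled Week 48.
- **SAP 11.1.2.** Whenever the extended visit is used, state that the regular-window MMRM will be presented. Before the data cutoff, state what triggers the extended visit and which estimate is the main one.
- **Same section.** Correct the pointer for the windowing rules from Appendix B to Appendix A.

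The cost is SAP wording and one rerun of models already programmed. The downside is that a few late values drop out of the interim Week 48 estimate; those subjects are then handled under the missing-at-random assumption that the MMRM already makes.

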11.3.4 Height and Weight

Height and weight will be measured with shoes off and before the dose of the study drug at each clinic visit during the Treatment Periods.

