10 STATISTICAL ANALYSIS

10.1 General Considerations

The Schedule of Assessments is provided in Section 3 of the CSP. The precision standards for reporting safety and efficacy variables are provided in an internal Biometrics document that specifies the programming rules including the precision for derived variables.

Continuous variables will be summarized using the following descriptive summary statistics: the number of subjects (n), mean, standard deviation (SD), median, minimum value (min), and maximum value (max).

Categorical variables will be summarized using counts and percentages. Percentages will be presented to 1 decimal place.

Baseline unless otherwise specified, is defined as the most recent non-missing measurement (scheduled or unscheduled) collected prior to the first dose of study drug in the parent study.

Note: for subjects who take Orkambi or Symdeko (branded as Symkevi in Europe) during the 28 days before the screening visit, the data collected at screening visit will not be used for baseline derivation for spirometry, sweat chloride and LCI.

Absolute change from baseline will be calculated as Post-baseline value – Baseline value.

Relative change from baseline will be calculated and expressed in percentage as $100\% \times (\text{Post-baseline value} - \text{Baseline value}) / \text{Baseline value}$.

Unscheduled visits: Unscheduled visit measurements will be included in analysis as follows:

- In scheduled visit windows per specified visit windowing rules
- In the derivation of baseline and last on-treatment measurements
- In the derivation of maximum and minimum values during TE period, and maximum and minimum change from baseline values during TE period for safety analyses
- In individual subject data listings as appropriate

Visit windowing rules: The analysis visit windows for protocol-defined visits are provided in Appendix A.

Incomplete/missing data will not be imputed, unless specified otherwise.

Outliers: No formal statistical analyses will be performed to detect or remedy the presence of statistical outliers, unless specified otherwise.

Multiplicity: There will be no multiplicity adjustment as no hypothesis test is planned for safety analysis, unless specified otherwise.

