10.3.1.2 Analysis of Secondary Efficacy Variables

10.3.1.2.1 Definition of Variables

Percent predicted FEV₁ (ppFEV₁): the ppFEV₁ value is the ratio of FEV₁ (L) and predicted FEV₁ (L), expressed as a percentage. See [Appendix C](#) for more details.

Sweat chloride (SwCl): the SwCl value for a given visit will be calculated as the mean of the non-missing sweat chloride measurements obtained on the left and right arms at that visit. If one of the two arm measurements at a time point is missing, the other will be used as the mean. A volume ≥ 15 μ L is required for an accurate determination of sweat chloride. Any results reported as having volume < 15 μ L will be considered missing for analysis purposes. Any sweat chloride values reported as < 10 mmol/L or > 160 mmol/L will be considered missing for analysis purposes.

Cystic Fibrosis Questionnaire-Revised (CFQ-R): the CFQ-R^{1,4,6} is a validated CF-specific instrument that measures quality-of-life domains. This study utilizes two different versions of CFQ-R:

- CFQ-R for Children ages 6 to 13
- CFQ-R for Parents/Caregivers

In both versions, specific questions belonging to a domain are scored 1, 2, 3, or 4. The CFQ-R domain score, e.g., physical domain score or respiratory domain score, is defined as a scaled score as follows:

Scaled score for a domain = $100 \times (\text{mean (scores of all questions in the domain)} - 1) / 3$,

where the score from a negatively phrased question is first reversed, i.e., reversed score = 5 – actual score, so that 1 always represents the worst condition and 4 the best condition. The (scaled) domain

score ranges from 0 (worst condition) to 100 (best condition). The scaled score for a specific domain will not be calculated if more than half of the questions in the domain have missing scores.

Body mass index (BMI): the BMI at each visit is calculated using the weight and height at each visit as follows:

$$\text{BMI} = \text{Weight (kg)} / [\text{Height (m)}]^2$$

BMI z-score: the BMI score, adjusted for age and sex, will be referred to as BMI-for-age z-score (BMI z-score). The BMI z-score will be calculated by using Centers for Disease Control and Prevention (CDC) growth charts⁷, with the age (in months) used for the calculation defined in Appendix A.

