10.3.1.2.2 Analysis Method

Absolute change in ppFEV₁ from baseline:

In the MMRM for the OLE efficacy period for Part A, the absolute change from baseline in ppFEV₁ will be analyzed using the MMRM approach based on the OLE-FAS for Part A. The model will include absolute change from baseline in ppFEV₁ as the dependent variable, and visit as the fixed effect, with baseline ppFEV₁ value and genotype group (F/F vs. F/MF) as covariates. The model will be estimated using restricted maximum likelihood. Denominator degrees of freedom for the *F*-test of fixed effects will be estimated using the Kenward-Roger approximation². An unstructured covariance structure will be used to model the within-subject errors. If the model estimation does not converge, a compound symmetry covariance structure will be used instead. Conditional on the observed data and covariates, missing data will be assumed to be missing at random; consequently, no imputation of missing data will be performed.

The estimated mean change from baseline in ppFEV₁ at each post-baseline visit, along with the corresponding 2-sided 95% confidence interval (CI) will be provided.

The analysis will be conducted with the clinic spirometry data only. An additional analysis may also be performed to include pooled spirometry data obtained in clinic and by Air Next Spirometer, if the Air Next Spirometry data are assessed to be reasonably consistent with clinic spirometry data.

Absolute change in sweat chloride from baseline:

Analysis of this PD variable will be based on an MMRM similar to the analysis of the absolute change in ppFEV₁ from baseline with the baseline sweat chloride included as a covariate instead of baseline ppFEV₁.

Absolute change in the CFQ-R respiratory domain score from baseline:

Analysis of this domain (child's version) will be based on an MMRM similar to the analysis of the absolute change in ppFEV₁ from baseline with the baseline CFQ-R respiratory domain score (child's version) included as a covariate instead of baseline ppFEV₁. The analysis will include clinic assessed CFQ-R RD score only. An additional analysis may be performed to include pooled CFQ-R RD score assessed at clinic and at home, if the home assessed data are reasonably consistent with the clinic assessed data.

Absolute change in BMI and BMI-for-age z-score from baseline:

Absolute change in weight and weight-for-age z-score from baseline:

Absolute change in height and height-for-age z-score from baseline:

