10.3.2.2.2 Analysis Method

Absolute change in ppFEV₁ from baseline:

For Part A data during the OLE efficacy period, the same model in Section 10.3.1.2.2 will be repeated. For Part B data during the OLE efficacy period, similar MMRM model will be applied based on the OLE-FAS. The model will include absolute change from baseline in ppFEV₁ as the dependent variable, and visit in Part B as the fixed effect, with baseline ppFEV₁ value and genotype group (F/F vs. F/MF) as covariates. The model will be estimated using restricted maximum likelihood. Denominator degrees of freedom for the *F*-test of fixed effects will be estimated using the Kenward-Roger approximation². An unstructured covariance structure will be used to model the within-subject errors. If the model estimation does not converge, a compound symmetry covariance structure will be used instead. Conditional on the observed data and covariates, missing data will be assumed to be missing at random; consequently, no imputation of missing data will be performed.

The estimated mean change from baseline in ppFEV₁ at each post-baseline visit, along with the corresponding 2-sided 95% confidence interval (CI) will be provided.

The analysis will be conducted with the clinic spirometry data only. An additional analysis may also be performed to include pooled spirometry data obtained in clinic and by Air Next Spirometer, if the Air Next Spirometry data are assessed to be reasonably consistent with clinic spirometry data.

Absolute change in sweat chloride from baseline:

Analysis of this PD variable will be based on an MMRM similar to the analysis of the absolute change in ppFEV₁ from baseline with the baseline sweat chloride included as a covariate instead of baseline ppFEV₁.

Absolute change in the CFQ-R respiratory domain score from baseline:

Analysis of this domain (child's version) will be based on an MMRM similar to the analysis of the absolute change in ppFEV₁ from baseline with the baseline CFQ-R respiratory domain score (child's version) included as a covariate instead of baseline ppFEV₁. The analysis will include clinic assessed CFQ-R RD score only. An additional analysis may be performed to include pooled CFQ-R RD score assessed at clinic and at home, if the home assessed data are reasonably consistent with the clinic assessed data.

Absolute change in BMI and BMI-for-age z-score from baseline;

Absolute change in weight and weight-for-age z-score from baseline;

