	< First Dose Date of Study Drug	≥ First Dose Date and ≤ End Date of TE Period	> End Date of TE Period
< First dose date of study drug	P	PC	PCA
≥ First dose date and ≤ End date of TE period	-	C	CA
> End date of TE period	-	-	A

P: Prior; C: Concomitant; A: Post

Imputation rules for missing and/or partial dates of non-pharmacological treatment/procedure will follow the same imputation rule.

▪ **Appendix C: Details of GLI Equations for Calculating ppFEV₁**

Percent predicted values will be calculated for parameters of FEV₁, FVC, FEV₁/FVC, and FEF_{25%-75%} using the Quanjer GLI-2012 Regression Equations and Lookup Tables.

The regression equations and lookup tables required to implement the Quanjer GLI-2012 predicted values are available in:

Philip H. Quanjer, Sanja Stanojevic, Tim J. Cole, Janet Stocks. Quanjer GLI-2012 Regression Equation and Lookup Tables (Version 7 April 2013). Global Lung Function Initiative. [online] Available at: <https://www.ers-education.org/guidelines/global-lung-function-initiative/spirometry-tools/it-engineers-and-manufacturers/> [Accessed Sep 22, 2020].

The instructions and tools on how to implement the Quanjer GLI-2012 equations are:

Philip H. Quanjer, Sanja Stanojevic, Tim J. Cole, Janet Stocks. Implementing GLI-2012 regression equations (Version 19 July 2015). Global Lung Function Initiative. [online] Available at: <https://www.ers-education.org/guidelines/global-lung-function-initiative/spirometry-tools/it-engineers-and-manufacturers/> [Accessed Sep 22, 2020].

Sanja Stanojevic. GLI-2012 - SAS Macro (Version 2, 7 April 2013). Global Lung Function Initiative. [online] Available at: <https://www.ers-education.org/guidelines/global-lung-function-initiative/spirometry-tools/sas-macro/> [Accessed Sep 22, 2020].

Data handling rule for spirometry is as follows:

- Input age and height with at least 2 decimal place
- Height collected at the respective visit should be used; if the height at the respective visit is not available, the last non-missing record will be used.
- For race, map the CRF reported Black or African American to Black, all other races in CRF (except White) are mapped to 'other'; multiple checks for race in CRF are also mapped to 'other'; white is a reference race in the equations and assumes 0 values for all race coefficients in the GLI equations.

▪ Appendix D: Imputation Rules for Missing AE Dates

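### Carrying an old height forward into the GLI equations tends to overstate post-baseline ppFEV₁ in growing children; the SAP sets no age limit on that height

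*SAP*

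**What the plan says.** SAP 10.3.1.2.1 defines the variable: "the ppFEV₁ value is the ratio of FEV₁ (L) and predicted FEV₁ (L), expressed as a percentage". Appendix C takes the predicted value from the GLI-2012 equations, with the instruction "Input age and height with at least 2 decimal place". Height should come from the same visit; otherwise, "if the height at the respective visit is not available, the last non-missing record will be used". No maximum gap is given, and the equation coefficients are cited but not printed.

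Age is handled differently. The derived-variable notes to Table 13-1 in Appendix A recalculate it: "Age (in years) at first dose date and post-baseline visit". Under the fallback, therefore, only height goes stale.

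Protocol 11.3.4 sets when height is taken: "Height and weight will be measured with shoes off and before the dose of the study drug at each clinic visit". Tables 3-1 and 3-2 mark spirometry and height at the same visits. For the main ppFEV₁ model, SAP 10.3.1.2.2 states: "The analysis will be conducted with the clinic spirometry data only". SAP 10.3.2.2.2 repeats this for the whole extension and adds an option: "An additional analysis may also be performed to include pooled spirometry data obtained in clinic and by Air Next Spirometer". Baseline is "the most recent non-missing measurement (scheduled or unscheduled) collected prior to the first dose of study drug in the parent study" (SAP 10.1).

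SAP 10.1 imputes nothing unless a rule says so; the height rule is such an exception. Sections 10.3.1.2.3 and 10.3.2.2.3 plan no sensitivity analysis.

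**The concern.** Subjects came from a parent study of children aged 6 through 11, and treatment here runs for up to 192 weeks, so most will be growing for much of the study. Measured FEV₁ reflects the child's size on the day. If the denominator is built on a smaller, earlier height, part of normal growth is counted as better lung function.

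The error has an expected direction and grows with the age of the carried height. It also sits inside the dependent variable of the MMRM, so the missing-at-random argument in the SAP does not cover it. At stake is a modest upward bias in a secondary endpoint that is reported as estimated change with a 95% confidence interval at each visit. The plan offers no way to see how often it occurred.

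**Working it through.** The documents state no figure on this point, so there is none to reproduce. The check is of direction and size.

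**Inputs from the documents.** ppFEV₁ = 100 × measured FEV₁ / predicted FEV₁. Age is current and height may be carried. Scheduled spirometry and height visits are 8 to 12 weeks apart in Part A and 12 weeks apart in Part B.

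**Assumptions, not in the documents.** Predicted FEV₁ is proportional to height to the power k, with k = 2 to 3; the carried height is 135 cm; growth is 5 to 7 cm/year; true ppFEV₁ is 95.

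**Formula.** At fixed FEV₁ and age, carried ppFEV₁ / true ppFEV₁ = (true height / carried height)^k. The excess in points is 95 × [((135 + growth × gap/52.18)/135)^k − 1].

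**Worked case.** 12 weeks at 5 cm/year gives 5 × 12/52.18 = 1.15 cm. With k = 2: 95 × [(136.15/135)² − 1] = 1.6 points.

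| Gap | Growth (cm/year) | k = 2 | k = 3 |
|---|---|---|---|
| 12 weeks | 5 | +1.6 | +2.4 |
| 12 weeks | 7 | +2.3 | +3.4 |
| 24 weeks | 5 | +3.3 | +4.9 |
| 24 weeks | 7 | +4.6 | +7.0 |

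**Wider assumptions.** With height 115 to 150 cm, k = 1.5 to 3 and ppFEV₁ 90, a 12-week gap gives +0.4 to +1.1 points at 2 cm/year, +0.8 to +2.2 at 4 cm/year and +1.2 to +3.3 at 6 cm/year. With no growth the error is zero.

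**Height measurement error.** Suppose a single height has a normal error with SD 0.3 to 0.8 cm. The chance that a 12-week-old recorded height is at or above the true current height is about 6% to 28% at 2 cm/year, 0.1% to 13% at 4 cm/year and under 0.1% to 4% at 6 cm/year. In those records ppFEV₁ is not inflated.

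**Change from baseline.** Take k = 2.2, height 130 to 136 cm, FEV₁ 1.5 to 1.8 L and predicted FEV₁ 1.65 L at 130 cm.
- True change: 98.8 − 90.9 = +7.9 points.
- Carried height after baseline (134.6 cm): +10.1 points.
- Carried height at baseline (129.3 cm): +6.8 points.

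The sign of the error in the endpoint therefore depends on which of the two heights was carried.

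**Visit mean.** The shift is roughly the share of affected records times the error per record. The share is not documented. If it were 1% to 10% with a 12-week gap, the shift would lie between 0.01 × 1.6 = 0.02 and 0.10 × 3.4 = 0.34 points. At 5% it would be 0.08 to 0.17.

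**The case against.** The strongest reply is that the rule will seldom be used. A missed clinic visit loses spirometry and height together, so no ppFEV₁ is computed and nothing is carried. The fallback needs valid spirometry without a height, for example at an unscheduled visit. A 24-week gap generally needs two successive heights missing with spirometry done at the second. This stands, and it is why the per-record figures must not be read as study-level effects.

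A reader might place the problem mainly in pandemic-affected visits and home spirometry. The documents support this only in part. The pooled home analysis is optional and conditional, the Week 144 interim uses clinic data only (SAP 11.1.2), and SAP 10.3.1.2.2 and 10.3.2.2.2 mention stadiometers supplied for home use. What remains open is whether a home height counts as the visit height under Appendix C.

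A reader might also infer that the rule always inflates the result. It does not: little growth, measurement error or a carried baseline height can remove or reverse the error. Even so, there is one baseline per subject against up to 17 scheduled on-treatment spirometry visits (9 in Part A, 8 in Part B), so upward errors have far more opportunities.

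Finally, interpolating between earlier and later heights would make a visit's value depend on future data. It could then disturb the commitment in SAP 10.3.2 that Part A estimates stay identical to those of the Part A analysis. That is a fair objection to interpolation, but not to a method that uses only past data.

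**Conclusion.** The point holds as a tendency. A height carried to a post-baseline visit overstates ppFEV₁ in expectation in a child who has grown, by about 1.6 to 3.4 points per affected record at 12 weeks. This rests on a positive height effect in equations the SAP does not print, and on the assumed height, growth, exponent and ppFEV₁ level. The effect on visit means cannot be derived from the documents; it is probably small, because the rule should rarely be triggered in the clinic-only model.

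It would be wrong to describe this as a bias in the trial's main outcome. The primary endpoint is safety, ppFEV₁ is one of several secondary endpoints, and the planned output is estimates with intervals and no multiplicity adjustment. This is a minor improvement, worth making because it is cheap and because the present rule hides how often it acts.

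**What to change.** In Appendix C, replace the fallback: when the visit height is missing, carry forward the last height-for-age z-score (already derived under SAP 10.3.1.2.1) and convert it to centimetres at the visit age. This uses only past data and assumes that the child keeps the same z-score over the gap. Use the filled height only in the GLI prediction, not in the height, BMI or z-score endpoints.

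State that a home stadiometer height from the same visit qualifies in the pooled home-spirometry analysis. Report how many heights were carried, at which visits and over what gap; if there are few, that count settles the matter.

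If Part A estimates already reported must stay identical, apply the new rule to Part B and show Part A as a sensitivity analysis.

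The cost is a few sentences in the SAP and a small programming step. The downside is a possible slight difference from the parent study's derivation and, if Part A is left unchanged, between the two Parts.
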